6.2 Criteria for Treatment, Retreatment and Dose Modifications

6.2.1 APR-246

This section outlines the requirements for proceeding with treatment with APR-246, and the protocol rules for APR-246 dose modification due to toxicity.

The

Table **4** describes the routine ECG requirements from screening through Cycle 4 for patients in Experimental Arm:

Table 4. ECG Requirements in Experimental Arm

Time Point	ECG, n	Timing
Baseline/Screening	Triplicate	Within 28 days of Cycle 1 Day 1
Cycle 1, Days 1-4	Triplicate	Pre-dose; Post dose (6 hrs. after start of infusion; ± 30 min)
Cycles 2+, Day 1	Triplicate	Pre-dose

At screening (baseline), 12-lead ECGs should be collected in triplicate to confirm QT interval does not exceed 470 msec. QT interval must be calculated from a mean of all three ECG readings using Fridericia's correction ($QTcF = QT/RR^{0.33}$).

During Cycle 1 ECG should be collected in triplicate prior to infusion of APR-246 and at the end of infusion of APR-246 (6 hours after start of infusion, ± 30 min) on Days 1 - 4. QTcF must be calculated from a mean of all three ECG readings to confirm it does not exceed 470 msec.

If a pre-dose ECG shows $QTcF \geq 470$ msec, the QTc reading should be confirmed by manual assessment using Fridericia's correction ($QTcF = QT/RR^{0.33}$). Serum concentrations of electrolytes should be monitored and corrected, if necessary. Additionally, concomitant medication should be reviewed and adjusted, if necessary. ECG may be repeated at any time, including the same day. APR-246 may only be administered when QTcF has returned to < 470 msec. If APR-246 is given on the same day, procedures outlined in the Schedule of Study Evaluations (Table 8) must be followed. If APR-246 cannot be administered on the same day, that dose must be omitted from the cycle.

If there is a significant change in QTcF, defined as either: a) increase > 60 msec from baseline (or pre-dose), or b) increase to an absolute value ≥ 501 msec, i.e. consistent with NCI CTCAE Grade 3 QTc prolongation, QTc prolongation must be confirmed by a manual assessment of the ECG, and using Fridericia's correction ($QTcF = QT/RR^{0.33}$). If confirmed, the therapy should be interrupted until a cause (electrolyte disorders or an effect of a concomitant medication) has been identified and addressed, and QTcF has returned to < 470 msec. If all other causes for clinically significant QT interval prolongation are excluded, APR-246 must be permanently discontinued.

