During subsequent cycles ECG should be collected in triplicate prior to infusion of APR-246 on Day 1 of each cycle. QTcF must be calculated from a mean of all three ECG readings to confirm it does not exceed 449 msec. If pre-dose QTcF is 450-469 msec, APR-246 may be administered, and additional triplicate ECG should be performed at the end of infusion (6 hours after start of infusion, ± 30 min). If post-dose ECG shows a significant change in QTcF, defined as either: a) increase > 60 msec from baseline (or pre-dose), or b) increase to an absolute value ≥ 501 msec, i.e. consistent with NCI CTCAE Grade 3 QTc prolongation, QTc prolongation must be confirmed by a manual assessment of the ECG, and using Fridericia's correction ($QTcF = QT/RR^{0.33}$). If confirmed, the therapy should be interrupted until a cause

(electrolyte disorders or an effect of a concomitant medication) has been identified and addressed, and QTcF has returned to < 470 msec. If all other causes for clinically significant QT interval prolongation are excluded, APR-246 must be permanently discontinued. If QTcF is unchanged or there is no significant change, additional ECG is not required during that cycle.

If repeated QTcF measurements show a stable QTcF < 450 msec, or if QTcF remains stable within the interval of 450 – 469 msec with no significant change at the end of infusion during several cycles of treatment, reducing the number of ECGs performed in the study may be discussed with the Medical Monitor.

If a patient starts treatment with another medication known to prolong QT interval at any time during the study therapy, an additional pre- and post-dose (6 hours after start of infusion, ± 30 min) ECG should be performed on the next treatment day. For patients who do not tolerate the protocol-specified dosing schedule, one dose level reduction is permitted (Table 5) in order to allow the patient to continue the study treatment. A second dose reduction could be permitted following discussion with the Sponsor and Medical Monitor.

Table 5. APR-246 Dose Levels

Dose Modification	APR-246 Dose
Starting Dose Level (DL)	APR-246 4.5 g/day 1.5 g (for first 45 minutes) + 3.0 g (for 5 hours 15 minutes)
One dose level reduction (DL-1)	APR-246 4.0 g/day 1.33 g (for first 45 minutes) + 2.67 g (for 5 hours 15 minutes)
Second dose level reduction (DL-2)*	APR-246 3.5 g/day 1.16 g (for first 45 minutes) + 2.34 g (for 5 hours 15 minutes)

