† Only applicable for patients with normal baseline absolute neutrophil count (ANC) and platelets. For patients with low (abnormal) baseline ANC and/or platelets that do not return to baseline (pre-cycle) after a clinically significant decrease following treatment, please contact the Medical Monitor.

‡ Common Terminology Criteria for Adverse Events (CTCAE) version 5.

Other Non-Hematological Toxicities

Parameter	Worst toxicity	Dose Modifications for APR-246
CNS – dizziness, dyskinesia and ataxia	Grade 1	Maintain dose level
	Grade 2	If resolved (to ≤ Grade 1) with medical therapy, continue same dose level If not resolved despite treatment interruption and maximal medical therapy, stop infusion and ↓ 1 dose level for subsequent dose
	Grade 3	Stop infusion and give medical therapy. If resolved (to ≤ Grade 1) with medical therapy, infusion may continue at the investigator’s discretion. ↓ 1 dose level for subsequent dose
	Grade 4	Permanently discontinue patient from APR-246.
Infusion Related Reaction	Grade 1	Maintain dose level.
	Grade 2	Maintain dose level; Symptomatic management (e.g., antihistamines, corticosteroids, narcotics, IV fluids)
	Grade 3	If resolved (to ≤ Grade 1) in < 4 hours with treatment interruption and medical therapy (e.g., antihistamines, corticosteroids, narcotics, IV fluids), continue same dose level and rate. If not resolved in < 4 hours despite treatment interruption and maximal medical therapy, stop infusion and ↓ 1 dose level for subsequent dose
	Grade 4	Permanently discontinue patient from APR-246.
Nausea/Vomiting/ Diarrhea	Grade 1	Maintain dose level
	Grade 2	If resolved (to ≤ Grade 1), then maintain dose level If not resolved despite maximal medical therapy, then ↓ 1 dose level
	Grade 3	If resolved (to ≤ Grade 1), then maintain dose level If not resolved despite maximal medical therapy, then ↓ 1 dose level
	Grade 4	Permanently discontinue patient from APR-246
Any Other Toxicity	Grade 3 or 4	Delay dose until resolution to ≤ Grade1, then ↓ 1 dose level

† Common Terminology Criteria for Adverse Events (CTCAE) version 5.

Treating physicians should use clinical judgment and may consult the Medical Monitor for guidance with dose modifications.

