6.2.2 Management of CNS Adverse Events

If a patient reports any clinical adverse event of any grade during the administration period of APR-246 that could be considered to originate from the CNS (e.g. dizziness, vertigo, nausea) then the patient will be given a rescue medication as per the institutional standard of care.

Dose modifications have been successfully used to manage potential CNS effects occurring during the infusion. For any clinical adverse event Grade ≥ 3 , the infusion should immediately be stopped, and if all symptoms resolve to CTCAE \leq Grade 1 within 2 hours, the infusion may be resumed at the same infusion rate. If the same symptoms do occur or increase in severity during re-challenge the infusion should be stopped.

If the event lasts longer than 2 hours, then the APR-246 infusion should be discontinued for that day, the remaining drug should be discarded, and toxicity should be managed according to recommendations in Table 6.

After an adverse event considered as related, a single level dose reduction of APR-246 is allowed. Dose reduction is recommended after any Grade ≥ 3 CNS AEs.

In prior studies, prochlorperazine 10 mg orally tid (three times daily) has been reported to be an effective treatment that may also be used prophylactically. When prochlorperazine is used prophylactically, start the day prior to the Day 1 and continue 10 mg tid to day 4 (as needed). The US label for prochlorperazine does not list QT prolongation as a known risk associated with use of this drug.

Re-escalation after dose reduction due to any APR-246-related toxicity may be permitted following discussion with the Medical Monitor.

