6.3 Concomitant Treatment

If patients experience prolonged myelosuppression they will be placed on infection prophylaxis per standard of care.

Patients may not receive any other drug to treat MDS while on study. Patients may continue their baseline medication(s) as long as they are not prohibited. Palliative and supportive care (e.g., anti-emetics, bisphosphonates) for disease related symptoms will be offered to all patients in the study per institutional practices. Adverse events will be treated

as clinically indicated. All concomitant medications that are currently in use or that become necessary during the study should be recorded.

Hydroxyurea may be administered before study start and up to the time of study randomization. At the investigator's discretion, for patients with significant leukocytosis during the early treatment cycles, hydroxyurea may be administered. The hydroxyurea should be discontinued as soon as clinically appropriate.

If the patient develops an acute infusion reaction (\geq Grade 2), the infusion must be stopped until the reaction is resolved to \leq Grade 1. Premedication (e.g., dexamethasone) may be used after the first cycle.

The prophylactic use of G-CSF is prohibited. Supportive use of G-CSF for treatment of cytopenias may be allowed at the discretion of the investigator per institutional practices.

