7.3.1.1 Days 1-10

Day 1 examinations marked * do not need to be repeated if already performed within 3 days prior to day 1 cycle 1.

- Transfusion log: must capture all transfusions beginning from 8 weeks prior to randomization to end of treatment/off treatment.
- Adverse Events: All adverse events since the last visit should be recorded. Even though pre-medicated, patients should be closely monitored.
- Concomitant medications.
- Physical examination: Day 1* weight, body surface area.
- ECOG performance status: Day 1.
- Vital signs. **Before infusion**, 2 hours into **each** infusion (± 30 min) and at EOI (± 30 min)
- Hematology: Day 1* hemoglobin, hematocrit, MCV, platelet count, blasts, WBC and WBC differentials.
- Blood chemistry: Day 1* sodium, potassium, BUN, glucose, ALT/AST, alkaline phosphatase, total protein, total bilirubin, albumin, creatinine, calcium, chloride and magnesium.
- ECG: Standard 12-lead ECG to be performed with patient in a semi-recumbent position; pre-dose (prior to the PK blood draw before the infusion) and at the end of infusion, per Table 10.
- Pharmacokinetics for APR-246: on Days 1, 2, 4, per Section 8.3

- APR-246 administration.
- Azacitidine administration. Administered daily for 7 consecutive days starting on Day 4 (Days 4 to 10 inclusive). The same route should be maintained over the 7-day treatment period (whichever route is used on Day 4, the other days should follow the same method route of administration). On Day 4 azacitidine is given immediately after APR-246 infusion.
- Pharmacokinetics for azacitidine: Day 4, per Section 8.3 (at selected sites only)

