8.4 ECG in Experimental Arm: ECG for APR-246

Table 10 describes the routine ECG requirements from screening through cycle 4:

Table 10. ECG Requirements in Experimental Arm

Time Point	ECG, number	Timing
Baseline/Screening	Triplicate	Must be within 28 days of C1D1
Cycle 1, Days 1-4	Triplicate	Pre-dose; Post dose (6 hrs. after start of infusion; ± 30 min)
Cycles 2+, Day 1	Triplicate	Pre-dose

If repeated QTcF measurements show a stable QTcF < 450 msec, or if QTcF remains stable within the interval of 450 – 469 msec with no significant change at the end of infusion during several cycles of treatment, reducing the number of ECGs performed in the study may be discussed with the Medical Monitor.

If a patient starts treatment with another medication known to prolong QT interval at any time during the study therapy, an additional pre- and post-dose (6 hours after start of infusion, ± 30 min) ECG should be performed on the next treatment day.

Please consult Section 6.2.1 for additional requirements for proceeding with treatment with APR-246.

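### The post-dose APR-246 ECG is timed from the start of infusion, so after a permitted 2 h pause its window closes 1.5 h before the infusion ends

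*Combined protocol and SAP*

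**What the plan says.** **ECG timing.** For Cycle 1, Section 6.2.1 asks for a triplicate ECG before each infusion and again "at the end of infusion of APR-246 (6 hours after start of infusion, ± 30 min) on Days 1 - 4". For later cycles, if the pre-dose QTcF is 450-469 msec, an "additional triplicate ECG should be performed at the end of infusion", with the same clock time in brackets. Table 4 and Table 10 (Section 8.4) give only the clock time; Table 10 reads "Post dose (6 hrs. after start of infusion; ± 30 min". The rule in 6.2.1 and 8.4 for a patient who starts another QT-prolonging drug also gives only the clock time. Section 7.3.1.1 uses the end-of-infusion label but defers to the table: "and at the end of infusion, per Table 10". Footnote m to the Schedule of Study Evaluations likewise sends the reader to Table 10.

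**Pauses.** Section 6.2.2 stops the infusion for a Grade 3 or higher event. If symptoms resolve to Grade 1 or less "within 2 hours, the infusion may be resumed at the same infusion rate". Beyond that limit the day's infusion is over: "If the event lasts longer than 2 hours, then the APR-246 infusion should be discontinued for that day". For infusion reactions of Grade 2 or higher, Section 6.3 says "the infusion must be stopped until the reaction is resolved to" Grade 1 or less, with no time limit.

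**Other end-of-infusion procedures.** Vital signs (Section 7.3.1.1 and footnote f) are due at end of infusion ± 30 min, with no clock time from start. Table 9 places an APR-246 PK sample at the end of the infusion on Days 1 and 4 of Cycles 1-3. Section 6.1.1 requires infusion start, stop and rate-change times to be recorded.

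**The concern.** Six hours is simply the planned infusion length, so the label and the clock time coincide until an infusion is paused. Because 6.2.2 resumes at the same rate, lost time is not made up: the end of infusion moves later and the ECG window stays where it was. A site following Table 10 then records a mid-dose ECG, and a site following the label records one outside the stated window.

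This ECG carries a decision. Under 6.2.1, a confirmed QTcF rise of more than 60 msec, or a value of 501 msec or more, interrupts APR-246. If no other cause is found, APR-246 is stopped for good. On the PK days, an in-window ECG after a pause is also separated in time from the end-of-infusion PK sample.

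**Working it through.** This is clock arithmetic. No sample-size or power calculation is involved.

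**Inputs**
- Loading step: 45 min ± 2 min (6.1.1).
- Maintenance step: 5 h 15 min ± 30 min, i.e. 315 ± 30 min (6.1.1).
- ECG window: 6 h ± 30 min after start, i.e. 330 to 390 min (6.2.1, Tables 4 and 10).
- Longest pause after which 6.2.2 allows resumption: 2 h = 120 min, at the same rate.

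**The plan's own figure, no pause**
- Nominal: 45 + 315 = 360 min = 6 h, which matches the stated ECG time.
- Fastest: 43 + 285 = 328 min = 5 h 28.
- Slowest: 47 + 345 = 392 min = 6 h 32. This is already 2 min past the close of the window, with no pause at all.

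**After a 2 h pause** (end = unpaused end + pause; gap = end − 390 min)
- Nominal: 360 + 120 = 480 min = 8 h; gap 480 − 390 = 90 min = 1.5 h.
- Fastest: 328 + 120 = 448 min = 7 h 28; gap 58 min.
- Slowest: 392 + 120 = 512 min = 8 h 32; gap 122 min = 2 h 02.

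**Pause that pushes the end past the window** (390 − unpaused end)
- Nominal: 390 − 360 = 30 min, so any pause over 30 min.
- Fastest: 390 − 328 = 62 min.
- Slowest: 390 − 392 = −2 min, so no pause is needed.

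**Separation from the end-of-infusion PK sample, nominal rate, 2 h pause**
- ECG at the close of the window: 8 h − 6 h 30 = 1.5 h before the sample.
- ECG at the opening of the window: 8 h − 5 h 30 = 2.5 h before the sample.

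**Search for a pause rule.** None of Sections 6.2.1, 6.2.2, 6.2.4, 6.3, 7.3 and 8.4, nor footnote m, re-times the ECG after a pause. The permission in 6.2.1 to repeat an ECG on the same day belongs to the paragraph on a raised pre-dose QTcF. Section 6.2.3 is the one partial exception: patients given QT-prolonging drugs must have an ECG on either side of the infusion. It gives no window and does not reach paused patients who receive no such drug. After a pause it also pulls away from the co-medication rule in 6.2.1, which keeps to 6 h from start.

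**The case against.** The strongest reply is that the intent is readable. The text of 6.2.1 puts the ECG at the end of infusion and adds the clock time in brackets, which is naturally taken as the nominal time. A site that waits for the true end serves the purpose and at worst logs a small timing deviation. This has force for 6.2.1, but less for Tables 4 and 10 and the co-medication rule, which give only the clock time, or for 7.3.1.1, which defers to Table 10.

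The second reply is that protection already exists. Cycle 1 has pre- and post-dose triplicates on each of four days, eight sets in all. Section 6.2.3 gives an infusion-anchored ECG to patients on QT-prolonging drugs, and Table 7 marks two of its four anti-emetics (ondansetron and dolasetron) as such. This stands, and it is a reason to rate the point minor.

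Three stronger readings are tempting, and the documents do not support them:
- A reader might infer that the QTcF peak is missed. The cardiac safety section (2.6.6) is redacted, and nothing available shows where the peak falls or how much QTcF would differ between an in-window ECG and one at the true end.
- A reader might infer a gap approaching 3.5 h from Table 6, which describes Grade 3 infusion reactions settling in under 4 "hours with treatment interruption and medical therapy". Whether that permits a longer pause is arguable: 6.2.2 sits under a CNS heading, but its wording covers any clinical adverse event and ends the day's infusion after 2 h. The point does not need the longer figure.
- A reader might conclude that no pause rule exists anywhere. The grid of Table 8 is not in the text, and the Pharmacy Binder and Laboratory Manual are not supplied, so a rule there cannot be excluded.

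**Conclusion.** The point holds as a small timing defect. The stated rule works for an uninterrupted infusion at nominal rate and misfires under a pause that the protocol itself permits: after 2 h, the window closes 1.5 h before the nominal end (58 min to 2 h 02 across the allowed rates). An ECG used for a stopping rule is then read mid-dose, while vital signs and the PK sample follow the actual end.

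The result assumes that the infusion resumes at the same rate, as 6.2.2 states, and that the step tolerances apply to infusing time, not to the pause. It concerns only experimental-arm infusions paused for more than about 30 min at nominal rate and then resumed, on Cycle 1 Days 1-4 and on later days when a post-dose ECG is triggered. The slowest allowed infusion also ends 2 min outside the window without a pause. The documents give no pause frequency, so neither the number of affected ECGs nor any missed QTcF rise can be determined. The primary analysis is not affected. Severity is minor; this is a cheap improvement.

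**What to change.** In Tables 4 and 10 and Sections 6.2.1, 7.3.1.1 and 8.4, time the post-dose triplicate ECG at the actual end of infusion ± 30 min (nominally 6 h after start), and say that this includes infusions paused and resumed. This is the rule already used for vital signs.

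For a nominal unpaused infusion the window stays at 5 h 30 to 6 h 30. After a 2 h pause it becomes 7 h 30 to 8 h 30, which does not overlap the current window. At the slowest allowed rate without a pause it becomes 6 h 02 to 7 h 02, so an ECG at the true end is in window.

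The cost is one sentence carried into five places. No ECG is added, and the stop time is already recorded. The one downside is a later ECG after a pause, on a day when end-of-infusion vital signs already follow the later stop time.

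### With a baseline QTcF below 410 msec, APR-246 can restart under the QT rule while the rise above 60 msec that stopped it is still present

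*Combined protocol and SAP*

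**What the plan says.** Section 6.2.1 takes its reference value from screening: "At screening (baseline), 12-lead ECGs should be collected in triplicate". The interruption rule begins "If there is a significant change in QTcF, defined as either: a) increase > 60 msec from baseline (or pre-dose"; its second arm is an absolute QTcF of 501 msec or more. Once either is confirmed by manual reading, APR-246 is held. The condition for resuming is this: "a cause (electrolyte disorders or an effect of a concomitant medication) has been identified and addressed, and QTcF has returned to < 470 msec". The rule ends: "If all other causes for clinically significant QT interval prolongation are excluded, APR-246 must be permanently discontinued". The paragraph for later cycles repeats the same release and the same discontinuation sentence.

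All the other numeric dosing limits in the section are absolute. For a pre-dose reading of 470 msec or more, "APR-246 may only be administered when QTcF has returned to < 470 msec", and "If APR-246 cannot be administered on the same day, that dose must be omitted from the cycle". From Cycle 2 the Day 1 pre-dose check reads "QTcF must be calculated from a mean of all three ECG readings to confirm it does not exceed 449 msec", followed by "If pre-dose QTcF is 450-469 msec, APR-246 may be administered, and additional triplicate ECG should be performed at the end of infusion". In those cycles the 60 msec test is worded for the post-dose ECG.

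**The concern.** Two different triggers share one numeric release. After a reading of 501 msec or more, getting below 470 msec forces a real fall. After a rise of more than 60 msec from a low baseline, it need force none: the ECG that stops treatment can already satisfy the number that restarts it.

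This matters because Section 2.8.1 lists QTc prolongation among the potential risks of APR-246, and the protocol itself classes a rise above 60 msec as a significant change. The route to restart through another cause is not remote. Table 7 suggests ondansetron and dolasetron for nausea and marks both as QT-prolonging. If such a drug is withdrawn and QTcF stays more than 60 msec above baseline but below 470, the QT rule is satisfied.

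**Working it through.** The plan gives no derived figure to reproduce; the check is arithmetic on its thresholds.

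**Inputs (all Section 6.2.1).** Let *b* be the screening triplicate mean QTcF and *q* the current QTcF, in whole msec.

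- Rise trigger: *q* − *b* > 60, so *q* ≥ *b* + 61.
- Absolute trigger: *q* ≥ 501.
- Numeric release, both triggers: *q* < 470, so *q* ≤ 469.
- Entry: the QTcF exclusion in Section 5.2 is an upper limit only (470 msec or more), so baselines below 410 are admissible.

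**Absolute trigger.** Going from 501 or more to 469 or less is a fall of at least 501 − 469 = 32 msec.

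**Rise trigger.** The rise persists when *q* > *b* + 60. This is compatible with *q* < 470 only if *b* + 60 < 470, so *b* < 410. In whole msec, *b* + 61 ≤ 469 gives *b* ≤ 408. At 409 only a fractional mean between 469 and 470 would qualify. The number of overlapping whole-msec values is 469 − (*b* + 61) + 1 = 409 − *b*.

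**Effect of the proposed release.** The ceiling becomes the smaller of 469 and *b* + 60.

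| Baseline *b* | Values that fire the rise trigger and meet the release | Count (409 − *b*) | Ceiling now | Ceiling with the fix |
|---|---|---|---|---|
| 380 | 441–469 | 29 | 469 | 440 |
| 385 | 446–469 | 24 | 469 | 445 |
| 390 | 451–469 | 19 | 469 | 450 |
| 400 | 461–469 | 9 | 469 | 460 |
| 405 | 466–469 | 4 | 469 | 465 |
| 408 | 469 | 1 | 469 | 468 |
| 409 or above | none | 0 | 469 | 469 |

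These are ranges of QTcF values, not patients or probabilities.

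**Cycle 2+ pre-dose ECG, the two readings side by side.** Take *b* = 390 and a Day 1 pre-dose of 455, a rise of 455 − 390 = 65.

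- If the general significant-change paragraph covers all cycles and both pre- and post-dose ECGs, a confirmed rise of 65 interrupts therapy.
- If it is the Cycle 1 rule, only the later-cycle paragraph applies: 455 lies in the 450–469 band, so dosing is allowed, with an ECG at the end of infusion.

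Paragraph order favours the second reading. The general paragraph follows the Cycle 1 instructions, and the later-cycle text restates the rule for post-dose ECGs. The first reading has support too, because the later-cycle text has no rule of its own for a pre-dose QTcF of 470 or more, so something has to carry forward.

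**The case against.** The case against making much of this is substantial, and most of it stands as a limit on size.

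- Restart always needs a cause that has been found and corrected; where other causes are excluded, APR-246 stops for good. A reader might infer that the rule lets patients with drug-induced prolongation go back on APR-246. It does not; only patients with another cause are concerned.
- In Cycle 1, ECGs are taken before and after each of the four infusions, so a persisting rise would fire the trigger again. This narrows the gap, but it leaves trigger and release giving opposite answers for the same reading. From Cycle 2 the routine ECG is Day 1 pre-dose only (Table 4), so after a restart the next routine one may be a cycle away.
- Table 6 delays dosing for any other Grade 3 or 4 toxicity until Grade 1 or less, then reduces the dose. That may apply if the event is judged treatment-related, which under Section 8.1.2.2 includes a possible relation. It does not reliably close the gap, because Table 6 covers treatment-related events while restart under the QT rule presupposes another cause.
- Section 6.2.3 requires ECGs before and after the infusion with QT-prolonging co-medication. That helps detection, but its own restart limit is also below 470 msec with no test against baseline.
- The cardiac safety overview (Section 2.6.6) is redacted, so any reason given there for absolute limits cannot be weighed.

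A reader might also infer that Section 6.2.1 contradicts itself on Cycle 2+ pre-dose rises. The documents do not show that. On the paragraph-order reading there is a gap and no contradiction. Even if the general paragraph carries forward, the permission to dose at 450–469 msec can be read as subject to the interruption rule. The supportable statement is that the text is unclear.

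**Conclusion.** The point holds as a narrow flaw in the restart rule. For baselines below 410 msec, the numeric release does not require the significant change to have resolved. The overlap is 29 msec values at a baseline of 380 and shrinks to one at 408; from 409 upwards there is none in whole msec.

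This takes baseline to be the screening triplicate mean and the rise to be confirmed manually. The documents give no distribution of baseline QTcF and no rate of corrected secondary causes, so the number of patients cannot be estimated; it is probably small. This is a minor patient-safety edit, worth making because it is cheap. The Cycle 2+ pre-dose question is a matter for clarification only.

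**What to change.** In both places in Section 6.2.1 where the release appears, require that QTcF is below 470 msec and no more than 60 msec above baseline, with baseline defined as the screening triplicate mean. Leave the cause condition and the permanent-discontinuation sentence as they are.

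The cost is one short edit, made twice, at the next amendment. No scheduled ECGs are added, since a reading is already needed to show the return below 470 msec. The downside is that a few restarts will be delayed or doses omitted, some only because of noise in the screening value, and a patient whose rise does not come down stays off APR-246 until it does. Nothing changes for baselines of 410 msec or above.

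Separately, the sponsor should say whether a Cycle 2+ pre-dose rise above 60 msec blocks dosing at 450–469 msec. A new hold procedure for that case is not recommended here. It could cost up to all four APR-246 doses of a cycle through baseline noise, could remove permanent discontinuation on one reading of the current text, and, if confined to that band, would leave pre-dose values of 449 msec or less untested.
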